6.3.3 Blinding

In Part 1 of this study (up to the Day 60 visit), a double-blinding technique will be used. MK-1654, palivizumab, and placebo will be prepared and administered in a blinded fashion by an unblinded pharmacist or medically qualified study personnel not otherwise involved in the conduct of the study. Unblinded study personnel should not have contact with participants for any study-related procedures/assessments postdose (prior to unblinding), including all safety follow-up procedures. The participant's legally acceptable representative,

the investigator(s), and Sponsor personnel or delegate(s) will be unaware of the study intervention assignments.

Part 2 of this study (time of unblinding through duration of participation in the study) is conducted as open-label therefore, the Sponsor, investigator, and participant/participant's legally acceptable representative will know the intervention administered.

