9.5 Analysis Populations

9.5.1 Efficacy Analysis Populations

Full Analysis Set (FAS) Population

The FAS population will serve as the primary population for the estimation of efficacy and for the estimation of incidence of RSV-associated disease. The FAS population consists of all randomized participants who receive at least 1 dose of study treatment. Participants will be included in the treatment group corresponding to the study treatment they were randomized to for the analysis using the FAS population.

For an episode of respiratory infection to be considered for evaluation of an efficacy endpoint for the analysis in the FAS population, a PCR result from the study central laboratory must be available for an NP sample that is collected between 0 and 12 days after symptom onset and between 7 days before and 12 days after symptom worsening. A sensitivity analysis will be conducted, which will include PCR results from NP samples collected within the timeframe mentioned above but not tested at the study central laboratory.

Per-Protocol Efficacy (PPE) Population

The PPE population will serve as a supportive analysis population for the estimation of efficacy and incidence of RSV-associated disease. To be eligible for inclusion in the PPE population, study participants must satisfy the following criteria:

- Receive a complete regimen of the correct clinical material corresponding to the treatment group the participants were randomized into (ie, 1 dose of MK-1654 for participants randomized to the MK-1654 group and 3 to 5 doses of palivizumab within the protocol-specified windows for participants randomized to the palivizumab group based on the date of enrollment and the predefined RSV season end date at each site),
- Have at least 1 follow-up visit/contact for assessment of RSV disease,

- Do not undergo 1) ECMO or 2) surgical intervention for CHD requiring cardiopulmonary bypass during the efficacy follow-up period (Day 150 or Day 180), and
- At any time during dosing or efficacy follow-up, do not experience a protocol deviation that may interfere with the assessment of protection against RSV infection conferred by MK-1654.

The final determination on important protocol deviations, and thereby the composition of the PPE population, will be made prior to the final database lock and will be documented in a separate memo.

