An additional analysis to estimate the efficacy of MK-1654 compared to palivizumab against RSV-associated MALRI from Day 1 through the end of the first RSV season will be performed. In this analysis, only infants who develop RSV-associated MALRI from Day 1 through the end of their RSV season will be defined as cases. In other words, the efficacy follow-up duration to be included in the analysis will be until either the date of the end of the RSV season or the Day 150 date, whichever occurs first, thereby only including the relevant period of risk of RSV disease for each infant. A similar analysis will be performed for the endpoint of RSV-associated hospitalization and the incidence of this endpoint along with the CI will be estimated for each treatment group. The key efficacy analyses for secondary endpoints are summarized in [Table 6](#).

For the efficacy analyses, cases of both RSV A and RSV B associated MALRI (or hospitalization) will be counted as endpoints. The efficacy of MK-1654 relative to palivizumab in RSV Season 1 against RSV A associated MALRI and RSV B associated MALRI will also be estimated separately. Similarly, the incidence of RSV A associated hospitalization and RSV B associated hospitalization in each treatment group will be estimated separately.

The incidence of RSV-associated MALRI and RSV-associated hospitalization through Day 180 postdose MK-1654 in RSV Season 2 and the corresponding 95% CIs will be computed:

- Separately by treatment group to which participants were randomized to in RSV Season 1, and
- Both treatment groups combined.

Table 6 Analysis Strategy for Key Efficacy Variables

Endpoint/Variable (Description, Time Point)	Primary vs. Supportive Approach	Statistical Method ^a	Analysis Population	Missing Data Approach
Secondary Endpoints				
Incidence of RSV-associated outpatient and inpatient MALRI from Day 1 through Day 150 post Dose 1 in RSV Season 1	P/S	Modified Poisson regression (estimate, 95% CI)	FAS/PPE	Missing data will not be imputed
Incidence of RSV-associated hospitalization from Day 1 through Day 150 post Dose 1 in RSV Season 1	P/S	Exact 95% CIs using the Chi-square distribution for Poisson variable (estimate, 95% CI)	FAS/PPE	Missing data will not be imputed
Incidence of RSV-associated outpatient and inpatient MALRI from Day 1 through the end of RSV Season 1	S	Modified Poisson regression (estimate, 95% CI)	PPE	Missing data will not be imputed

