Incidence of RSV-associated hospitalization from Day 1 through the end of RSV Season 1	S	Exact 95% CIs using the Chi-square distribution for Poisson variable (estimate, 95% CI)	PPE	Missing data will not be imputed
CI=confidence interval; FAS=full analysis set; MALRI=medically attended lower respiratory infection; P=primary approach; PPE=per-protocol efficacy; RSV=respiratory syncytial virus; S=supportive approach. ^a The statistical methods are described in Section 9.6.1.				

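### The supportive season-limited efficacy analyses are planned only in the per-protocol set, whose dosing criterion differs by arm, so they have no as-randomized version

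*Combined protocol and SAP*

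**What the plan says.** Section 9.5.1 ranks the two efficacy sets. For the FAS: "The FAS population will serve as the primary population for the estimation of efficacy and for the estimation of incidence of RSV-associated disease". It takes every randomized infant with at least one dose, analysed as randomized. For the other set: "The PPE population will serve as a supportive analysis population for the estimation of efficacy and incidence of RSV-associated disease".

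The PPE regimen criterion differs by arm: "1 dose of MK-1654 for participants randomized to the MK-1654 group and 3 to 5 doses of palivizumab within the protocol-specified windows". The number of palivizumab doses required depends on the enrollment date and the site's predefined season end. The Day 28 placebo dose of the MK-1654 arm is not named. Three further criteria apply to both arms: at least one follow-up contact, no ECMO or bypass surgery during efficacy follow-up, and no deviation judged to interfere with assessing protection.

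Table 6 lists the two Day 150 analyses under FAS/PPE. It lists two further rows, "Incidence of RSV-associated outpatient and inpatient MALRI from Day 1 through the end of RSV Season 1" and "Incidence of RSV-associated hospitalization from Day 1 through the end of RSV Season 1", as supportive and under PPE only. The text of Section 9.6.1 names no population for them. It says that "the efficacy follow-up duration to be included in the analysis will be until either the date of the end of the RSV season" or Day 150, whichever is earlier.

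On timing, Section 9.5.1 states: "The final determination on important protocol deviations, and thereby the composition of the PPE population, will be made prior to the final database lock". Section 6.3.3 states: "Part 2 of this study (time of unblinding through duration of participation in the study) is conducted as open-label".

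**The concern.** The season-limited analysis is the one that restricts follow-up to the time when each infant is exposed to RSV. As planned, it exists only in a set selected by what happens after randomization, and the selection rule is heavier in one arm.

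A palivizumab infant must attend on time again and again while at risk. If an RSV illness makes a dose late or missed, the regimen criterion removes both infant and case. An MK-1654 infant with the same illness on the same day still meets that criterion. No rule in Section 9.5.1 retains such an infant or keeps the follow-up before the missed dose.

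At stake are the season-limited relative efficacy for MALRI and the season-limited palivizumab incidence for hospitalization. A reader of those results could not tell the size or the sign of any distortion, because there would be no FAS result over the same window to set beside them.

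**Working it through.** **Inputs from the documents**

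- 500 infants per arm, PPE attrition 10%, not split by arm or case status (Section 9.9.1).
- Incidence 4.5% for MK-1654 and 6.0% or 7.5% for palivizumab: the Table 8 rows with 25% and 40% relative efficacy, which bound the expected range in Section 9.9.1. They are Day 150 figures, used here as an illustration for the season-limited window.
- Palivizumab doses 3 to 5 are due 28 to 32 days after the previous dose (Section 1.3.1.3).

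**Reproducing Table 8**

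With n = 500 × 0.90 = 450 per arm and d = n × incidence, the exact Poisson limits are χ²(0.025; 2d)/(2n) and χ²(0.975; 2d+2)/(2n). They give 0.028 to 0.069 at 4.5%, 0.040 to 0.087 at 6.0% and 0.052 to 0.105 at 7.5%, all as printed.

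For efficacy, simulated trials with variance of the log relative risk (1−p1)/(n·p1) + (1−p2)/(n·p2) give mean limits of −37.8 to 55.8 for the 25% row (printed −35.9 to 56.5) and −6.0 to 64.0 for the 40% row (printed −4.6 to 64.5). The plan's figures are sound under a loss that is the same in both arms and unrelated to outcome.

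**Effect of selection**

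Assumptions: palivizumab loses a share f of cases and g of non-cases; MK-1654 loses both equally, so its rate stays 4.5%. The documents give no values for f or g.

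Palivizumab PPE rate q = C(1−f) / [C(1−f) + (500−C)(1−g)], with C = 30 at 6.0% or 37.5 at 7.5%. Efficacy = 1 − 0.045/q.

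Example: C = 30, f = 20%, g = 10% gives q = 24/(24 + 423) = 5.37% and efficacy = 1 − 4.5/5.37 = 16.2%.

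| f (cases lost) | g (non-cases lost) | True 25% becomes | True 40% becomes |
|---|---|---|---|
| 10% | 10% | 25.0% | 40.0% |
| 20% | 10% | 16.2% | 33.1% |
| 20% | 5% | 11.8% | 29.6% |
| 30% | 10% | 4.9% | 24.1% |
| 30% | 5% | −0.2% | 20.2% |
| 10% | 20% | 32.8% | 46.2% |
| 0% | 15% | 35.6% | 48.3% |

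A 20% loss of cases is 6 infants out of 30, or 7.5 out of 37.5. Equal loss leaves the estimate unchanged, excess loss of cases lowers it, and excess loss of non-cases raises it.

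For scale, the closed-form 95% interval at 450 per arm is −31.5% to 57.2% for the 25% row. After f = 20%, g = 10% it is −49.2% to 52.9% around 16.2%. The shift of about 9 points is well inside sampling error, but it would be systematic.

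**Same illustration in the FAS**

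At 500 per arm the closed form gives 25.0% (−27.7 to 56.0) and 40.0% (0.3 to 63.9), with no exclusion for missed or late doses.

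**The case against.** A reader might infer four stronger things. The documents do not support them.

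*That the trial loses its randomized comparison.* It does not. Section 9.6.1 introduces the season-limited work as additional, and Table 6 marks both rows supportive. The window closes at season end or Day 150, whichever is earlier, so every in-season case already lies inside the Day 150 window, which is analysed in the FAS as the primary approach. The study tests no hypotheses (Section 9.3).

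*That MK-1654 infants qualify for PPE on Day 1.* Only the dose criterion is settled then. The other three criteria run into or through follow-up and bind both arms.

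*That the bias must run against MK-1654 and be large.* If a further 25% of palivizumab cases were lost with no further loss of non-cases, the rate would be 20.25/(20.25 + 423) = 4.57% and efficacy 1.5% instead of 25%. That assumes loss among cases only. Other illnesses also delay doses, which removes non-cases, and well infants may skip visits. The mechanism is plausible but not spelled out. The window is short, and Section 8.13.5 requires the Day 28 visit at the site. The 72-hour fever rule in Section 8.1.8.1 speaks of rescreening, so its reach to later doses is unclear. Section 8.13.5 allows home or alternate-site visits otherwise. A case after the last dose cannot cause a missed dose.

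*That PPE membership is decided late with arm and outcome known.* Section 9.5.1 sets a latest date and requires a memo. The dose criterion is objective, and only the interfering-deviation criterion calls for judgement. Appendix 2 (Section 10.2) blinds those involved in administering treatment or in clinical evaluation to the laboratory data. What stands is that the arm is known from the Day 60 visit and that nothing requires the judgement to be made without it.

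The hospitalization row gives an incidence for each arm and no ratio, so the concern there is the palivizumab incidence only.

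**Conclusion.** The point stands in limited form. Both season-limited rows of Table 6 are confined to a set whose regimen criterion is met at once in one arm and only during the at-risk period in the other. They therefore have no as-randomized version, at odds with the primary role that Section 9.5.1 gives the FAS.

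The possible bias is in the season-limited MALRI efficacy and the season-limited palivizumab hospitalization incidence. Its direction is not fixed and its size cannot be derived from the documents. The illustrative fall from 25% to 11.8%–16.2%, or from 40% to 29.6%–33.1%, rests on assumed losses of 20% of palivizumab cases and 5% to 10% of non-cases, with MK-1654 losing both equally. The primary Day 150 FAS analyses are untouched. The point is worth correcting because the remedy is cheap, not because the main result is at risk.

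**What to change.** In Table 6, list both season-end rows as FAS/PPE, with FAS as the main version and PPE as supportive, and name the populations in the matching text of Section 9.6.1. Report PPE exclusions by arm, reason and timing relative to any RSV episode.

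A sensible addition to Section 9.5.1 is to make the judgement-based deviation decisions from listings that show neither arm nor RSV result.

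A PPE version that censors at the first missed or late dose and keeps earlier cases is optional only. That censoring would fall almost entirely on the palivizumab arm and could itself be informative, so it should not replace the FAS version.

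The cost is SAP wording and a rerun of programs already needed, on data already collected. The opening of Section 9 provides for changes to nonconfirmatory analyses to be documented in the supplemental SAP before unblinding/final database lock.

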5.2 Exclusion Criteria

The participant must be excluded from the study if the participant meets any of the following criteria:

Medical Conditions

1. Requires mechanical ventilation at time of enrollment.
2. Has a life expectancy <6 months.
3. Has known hepatic or renal dysfunction, or chronic seizure disorder.
4. Is hospitalized at the time of randomization unless discharge is expected within 7 days after randomization.
5. Has severe immunodeficiency or is severely immunocompromised, including but not limited to:
 - AIDS (CD4 percentage <25%, or history of AIDS-Defining Condition),
 - leukemia, myeloproliferative disorder, or other malignancy and receiving or expected to receive chemotherapy during the study,

- status post solid-organ or bone marrow transplantation and on a systemic immunosuppressive regimen,
- OR
- severe combined immunodeficiency.
6. Has known hypersensitivity to any component of MK-1654 (refer to the IB for a list of components) or palivizumab (refer to the Synagis™ label for a list of components). (See Appendix 7.1 for specific requirements for participants in France.)
 7. Has received other investigational agents at any time before study entry.
 8. Is anticipated to have either of the following within 60 days after randomization: 1) surgical correction resulting in hemodynamically insignificant CHD or 2) cardiac surgical procedure that will require cardiopulmonary bypass.
 9. Requires ECMO or continuous positive airway pressure at the time of enrollment or anticipated within 60 days after randomization.
 10. Has an anticipated or planned cardiac transplantation to occur during the course of this study.
 11. Has a bleeding disorder contraindicating intramuscular administration.
 12. Has had a recent illness with rectal temperature $\geq 100.5^{\circ}\text{F}$ ($\geq 38.1^{\circ}\text{C}$) or axillary temperature $\geq 100.0^{\circ}\text{F}$ ($\geq 37.8^{\circ}\text{C}$) within 72 hours predose. (See Appendix 7.2 for specific requirements for participants in the Czech Republic.)

Note: If the participant meets this exclusion criterion, the RSV Season 1 or RSV Season 2 Day 1 visits may be rescheduled for a time when this criterion is not met.

13. Has symptoms of LRI (defined in Section 8.2.1) within 7 days predose (Section 8.13.1).

Note: If the participant meets this exclusion criterion, the RSV Season 1 or RSV Season 2 Day 1 visits may be rescheduled for a time when this criterion is not met.

Prior/Concomitant Therapy

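### The PPE population excludes every infant who has ECMO or CHD bypass surgery during efficacy follow-up, so RSV cases that precede or lead to the procedure are dropped with the infant

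*Combined protocol and SAP*

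**What the plan says.** Section 9.5.1 introduces the PPE criteria as conditions of membership: "To be eligible for inclusion in the PPE population, study participants must satisfy the following criteria". The third condition is "Do not undergo 1) ECMO or 2) surgical intervention for CHD requiring cardiopulmonary bypass during the efficacy follow-up period (Day 150 or Day 180"). ECMO stands there without any restriction by cause. Neither Section 9.5.1 nor Section 9.6.1 keeps an endpoint episode that began before the procedure, and neither replaces exclusion by censoring.

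The roles of the two populations are clear: "The FAS population will serve as the primary population for the estimation of efficacy", while "The PPE population will serve as a supportive analysis population for the estimation of efficacy and incidence of RSV-associated disease". FAS membership carries no ECMO or surgery condition: "The FAS population consists of all randomized participants who receive at least 1 dose of study treatment".

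Table 6 plans both Day 150 endpoints in FAS and PPE. Two further rows, "Incidence of RSV-associated outpatient and inpatient MALRI from Day 1 through the end of RSV Season 1" and "Incidence of RSV-associated hospitalization from Day 1 through the end of RSV Season 1", name the PPE alone. Section 9.6.1 ends follow-up for those two analyses at the close of the season or at Day 150, whichever is earlier.

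The only explanation the plan gives for treating these procedures specially is in Section 4.3: palivizumab serum concentration falls after them. Exclusion criterion 8 in Section 5.2 screens out cardiac surgery only if it is foreseen early ("Is anticipated to have either of the following within 60 days after randomization"), and criterion 9 does the same for ECMO. Sections 4.1 and 6.3.2 plan at least 100 infants with CHD.

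**The concern.** A per-protocol population should not be selected on a consequence of the outcome it measures. ECMO can be the result of RSV respiratory failure. In such an infant the endpoint comes first, the procedure follows, and the rule then removes both infant and event. For bypass surgery the problem is mainly waste: an RSV case on Day 20 is deleted because of an operation on Day 140, although the antibody loss described in Section 4.3 cannot have affected Day 20.

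At stake is the reading of the supportive PPE results. Hospitalization is the most exposed endpoint, because it is reported as an incidence within each arm and because infants who reach ECMO through RSV are severe cases. The two end-of-season analyses are the weakest spot, since no FAS version of them is tabulated.

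**Working it through.** **1. Rule against rationale.** Section 4.3 concerns drug concentration after the procedure. The rule in Section 9.5.1 acts on all follow-up, before and after. Follow-up before the procedure has no stated reason for removal.

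**2. Window against analysis period.** The exclusion window runs to Day 150 or Day 180. The end-of-season analyses stop at season end if that comes before Day 150. An infant whose season closed earlier can thus be removed for a procedure that took place after the analysed period had ended.

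**3. Reproducing Table 8.** Inputs from Section 9.9.1: 500 per arm, 10% PPE attrition (500 × 0.9 = 450), MALRI incidence 15% without prophylaxis, efficacy 70% for MK-1654 and 60% for palivizumab. Incidences are 0.15 × 0.30 = 0.045 and 0.15 × 0.40 = 0.06. Exact Poisson limits at n = 450 are (0.0276, 0.0693) and (0.0395, 0.0873), matching the stated (0.028, 0.069) and (0.040, 0.087). For efficacy, the stated interval is 25.0% (−35.9, 56.5). Averaging the limits over 20,000 simulated trials gives (−37.7, 55.9), which agrees within what 1000 simulations would allow.

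**4. Effect of deleted cases on efficacy.** Expected cases are 450 × 0.045 = 20.25, taken as 20, and 450 × 0.06 = 27. Efficacy is 100 × {1 − (c_M/n_M)/(c_P/n_P)}, and the variance of the log ratio is 1/c_M − 1/n_M + 1/c_P − 1/n_P. This is unadjusted and uses participants in place of person-time. Each deletion removes one case and one infant. The number deleted is an assumption, varied from 0 to 3 per arm.

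| Deleted from MK-1654 | Deleted from palivizumab | Efficacy, % (95% CI) |
|---|---|---|
| 0 | 0 | 25.9 (−30.1, 57.8) |
| 1 | 0 | 29.5 (−25.0, 60.2) |
| 2 | 0 | 33.0 (−19.8, 62.6) |
| 3 | 0 | 36.6 (−14.6, 65.0) |
| 0 | 1 | 23.2 (−35.5, 56.5) |
| 0 | 2 | 20.4 (−41.3, 55.1) |
| 0 | 3 | 17.2 (−47.7, 53.6) |
| 1 | 1 | 26.9 (−30.1, 59.0) |

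One case lost from one arm moves the estimate by 29.5 − 25.9 = 3.6 points upward (MK-1654) or 25.9 − 23.2 = 2.7 points downward (palivizumab). The interval is 57.8 + 30.1 = 87.9 points wide.

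**5. Effect on arm-specific incidence.** The documents give no hospitalization rate, so event counts of 3, 5 and 10 in 450 are assumptions. Deleting one case with its infant changes 3/450 = 0.67% to 2/449 = 0.45%, 5/450 = 1.11% to 4/449 = 0.89%, and 10/450 = 2.22% to 9/449 = 2.00%. With two deletions the middle figure falls to 3/448 = 0.67%. Every such deletion lowers the reported incidence, and the fewer the events, the larger the relative drop. For scale, the exact 95% interval for 5 in 450 is 0.36% to 2.59%.

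**The case against.** The strongest reply is that little hangs on this. The FAS is primary, retains every such infant and event, and there is no hypothesis test. The exclusion is prespecified, worded the same for both arms, and linked to a recognised loss of antibody. All of that stands and limits the weight of the point. It does not justify discarding events that came before the loss.

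A reader might go further than the documents allow in three ways.

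- **Bias toward no difference.** One might expect the less protected arm to lose more cases and the contrast to shrink. Efficacy is a ratio: if the same fraction f of cases is removed in each arm, (1 − f)R_t / {(1 − f)R_p} = R_t/R_p, apart from a trivial change in denominators. Shrinkage requires palivizumab to lose a larger share of its cases, and nothing in the documents says that it would. Losing one case per arm moves the estimate the other way, from 25.9% to 26.9%.
- **A loss visible nowhere.** Because season-limited follow-up never passes Day 150, each case it counts is also a Day 150 case, and the FAS analysis at Day 150 keeps it if it meets the same PCR rules. What is missing is an FAS version of the two end-of-season rows.
- **A substantial number of affected infants.** Criterion 8 leaves surgery after Day 60 possible, and the schedules of activities provide for post-surgery follow-up. No document says how many of the CHD infants will have bypass, how often ECMO will occur, or that RSV illness will delay surgery.

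It can also be objected that changing the third criterion alone would do harm. The first PPE criterion requires a complete regimen: one dose for MK-1654, three to five in-window doses for palivizumab. A palivizumab infant who misses a window because of the procedure would still be dropped, while an MK-1654 infant would stay. That objection is right, and the fix has to deal with it.

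**Conclusion.** The criterion is faulty as written. It conditions PPE membership on an event that can follow from the endpoint, and it discards valid earlier data. Deleting RSV cases that led to ECMO understates arm-specific incidence in the PPE. The effect on relative efficacy can go either way, depending on which arm loses cases.

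The consequence is confined to supportive analyses; the primary FAS results at Day 150 do not change. The size cannot be derived from the documents. Under the Table 8 planning values it is about 3 efficacy points per MALRI case lost from one arm, small beside an interval about 88 points wide, and proportionally larger for rarer endpoints such as hospitalization. This rests on assumed counts of deleted cases and on an unadjusted calculation by participant. The end-of-season rows deserve most attention, because they exist only in the PPE and the exclusion window can outlast the period they cover.

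**What to change.** The changes are to the statistical plan only; nothing in clinical management is affected.

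1. In Section 9.5.1, replace the third PPE criterion by censoring at the date of ECMO or bypass, identically in both arms. Count an RSV episode with onset before that date as a case, even if it led to the procedure.
2. Use the same censored person-time for the log follow-up offset in the MALRI model and for the exact Poisson incidence of hospitalization. Section 9.6.1 defines person-time for MALRI but does not spell out the denominator for hospitalization.
3. For these infants, apply the complete-regimen criterion only to doses due before the procedure, so that differing dose numbers do not make retention unequal between arms.
4. Add FAS rows to Table 6 for the two end-of-season analyses.

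The cost is a few sentences and two table rows, settled before database lock. The existing rule already needs the procedure date to decide whether the procedure fell within follow-up. The drawbacks are that a few infants contribute partial follow-up to the PPE, and that censoring at surgery may itself be mildly informative if illness influences when surgery takes place.
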